4.2.8.5 Physical examination

No separate summaries of physical examination findings will be produced since there are no physical examination results reported outside of AE reporting.

4.2.9 Pharmacokinetics and immunogenicity

4.2.9.1 Analysis of pharmacokinetics

All analyses of PK variables will be based on the PK analysis set as defined in [Section 2.1.3](#).

Serum tezepelumab concentrations will be summarised over time for the on-study-period using descriptive statistics (for the tezepelumab group only).

Serum samples for PK are scheduled to be collected at weeks 0, 4, 12, 24, 36, 52, 64 and at the premature IP discontinuation visit, where appropriate. Data will be assigned to weeks based on the windows defined in [Section 3.1.5](#).

The following criteria will also apply for data to be included in the summary table:

- Only pre-dose samples at week 0.
- Only pre-dose samples at weeks 4, 12, 24 and 36 that were also between ≥ 21 and ≤ 35 days post the previous dose.
- Only samples that were taken between ≥ 21 and ≤ 35 days post the previous dose for week 52.
- All samples for week 64 that were taken within the visit window defined in [Section 3.1.5](#).

For descriptive statistics of tezepelumab concentrations:

- If, at a given time point, 50% or less of the concentrations are non-quantifiable (NQ), the geometric mean, coefficient of variation (CV), arithmetic mean and SD will be calculated by substituting the lower limit of quantification (LLOQ) divided by 2 for values which are NQ.
- If more than 50%, but not all, of the concentrations are NQ, the geometric mean, CV, arithmetic mean and SD will be reported as not calculable (NC)
- If all the concentrations are NQ, the geometric mean and arithmetic mean will be reported as NQ and the CV and SD as NC
- The median, minimum and maximum will also be reported.

The LLOQ of tezepelumab in serum will be 0.010 $\mu\text{g/mL}$.

If appropriate, descriptive statistics of tezepelumab concentrations over time will also be presented by ADA category (treatment-emergent ADA positive, non-treatment-emergent ADA positive, ADA negative, where treatment emergent for ADA is defined below in [Section 4.2.9.2](#)), and separately for adults and adolescents.

The PK data may be merged with those from other clinical studies for a population-based meta-analysis. If performed, results of the meta-analysis will be presented in a separate pharmacometrics report outside of the CSR, and this is not considered further in this SAP.

4.2.9.2 Analysis of immunogenicity

All analyses of immunogenicity variables will be based on the safety analysis set as defined in [Section 2.1.3](#).

The number of ADA positive subjects at each visit will be summarised by treatment group for the on-study period. Descriptive statistics including number of subjects, median, lower and upper quartile and range of the actual ADA titres by treatment group and visit, where possible, will be provided.

The ADA status across the study for each subject will also be classified and summarised by treatment group. Specifically, the following ADA results will be evaluated as number and proportion of subjects in cohorts together with corresponding titre summaries. However, if the number of ADA positive subjects in the safety analysis set is small then the ADA variables may be listed only in the CSR:

- Subjects who are ADA positive at any time including baseline (ADA prevalence).
- Subjects who are ADA positive at baseline only.
- Subjects who are ADA positive at baseline and positive in at least one post baseline measurement.
- Subjects who are ADA positive at baseline regardless of post-baseline result.
- Subjects who are ADA positive post-baseline.
- Subjects who are ADA positive post-baseline and ADA negative at baseline (treatment induced ADA)
- Subjects who are persistently positive; persistently positive is defined as having at least 2 post-baseline ADA positive measurements (with ≥ 16 weeks between first and last positive) or an ADA positive result at the last available post-baseline assessment.
- Subjects who are transiently positive; transiently positive is defined as having at least one post-baseline ADA positive measurement and not fulfilling the conditions for persistently positive.
- Subjects with treatment boosted ADA, defined as baseline positive ADA titre that was boosted to a 4 fold or higher level following IP administration
- Subjects with treatment emergent ADA (ADA incidence): defined as the sum of treatment induced ADA and treatment boosted ADA.

For ADA summaries at a single time point (e.g. baseline ADA or by visit) the corresponding titre summary will be based on the titre of the positive sample for that particular visit.

The ADA status across the study will also be summarised for the age subgroups at study entry: adults (≥ 65), adults (≥ 18 to < 65) and adolescents (≥ 12 to < 18).

For summaries across visits (e.g. ADA positive at any visit) the corresponding titre summaries will be based on the maximum titre of all positive samples for each subject.

Neutralizing ADA evaluations will be conducted on confirmed ADA positive samples. The test sample is deemed positive or negative for the presence of nAb to tezepelumab relative to a pre-determined (in assay validation) statistically derived cut point. The number and proportion of subjects who are nAb positive at any time will be evaluated.

If appropriate, the association of ADA status across the study with primary and key secondary efficacy, biomarkers and AEs/SAEs may be evaluated.

4.2.9.3 Exposure-response analyses

The subgroup analyses described below will be produced to characterise the exposure-response relationship.

- **Weight quartiles**

A similar negative binomial model will be fitted as for the primary analysis with additional factors for the subgroup variable and the treatment by subgroup interaction. This model will be used to estimate the treatment effect and its 95% CI within each of the subgroup categories, which will be tabulated and summarised graphically using a forest plot. The overall treatment effect will be displayed on the forest plot:

A similar MMRM model will be fitted as for the key secondary endpoint pre-BD FEV₁ with additional factors for the subgroup variable and the treatment by visit by subgroup interaction (as well as lower order interaction terms including these factors). This model will be used to estimate the treatment effect and its 95% CI within each of the subgroup categories at Week 52, which will be tabulated and summarised graphically using a forest plot. The overall treatment effect at Week 52 will be displayed on the forest plot. Adjusted means from this model will additionally be summarised graphically over time.

- **Drug concentration exposure quartiles**

Tezepelumab subjects will be grouped according to drug concentration quartiles. The treatment groups referred to in the following analyses will be the drug concentration quartiles and placebo. Each drug concentration quartile will be compared against the overall placebo group.

A similar negative binomial model will be fitted as for the primary analysis. This model will be used to estimate the treatment effect and its 95% CI for each drug concentration quartile, which will be tabulated and summarised graphically using a forest plot. The treatment effect for each drug concentration quartile will be displayed on the forest plot:

A similar MMRM model will be fitted as for the key secondary endpoint pre-BD FEV₁. This model will be used to estimate the treatment effect and its 95% CI for each drug concentration quartile at Week 52, which will be tabulated and summarised graphically using a forest plot. The treatment effect for each drug concentration quartile at Week 52 will be displayed on the forest plot. Adjusted means from this model will additionally be summarised graphically over time.

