4.3 Justification for dose

A 210 mg Q4W dosing regimen was selected for the Phase 3 studies based on efficacy data and an exposure-response analysis from the Phase 2b Study CD-RI-MEDI9929-1146 using population PK/PD methodology. The population PK model of tezepelumab was developed based on all available data from 5 Phase 1 studies (Study 20070620, Study 20080390, Study 2010118, Study D5180C00003, Study D5180C00002), and 2 Phase 2 studies (Study D5240C00001 and Study CD-RI-MEDI9929-1146). The exposure-response analysis was based on the Phase 2b Study CD-RI-MEDI9929-1146.

Analysis of data from the phase 2b study identified a statistically significant exposure-response against the primary efficacy endpoint of AAER and the pharmacodynamic (PD) endpoint of

FENO. These relationships indicate that the dose of 70 mg Q4W is a sub-optimally effective dose and the dose of 210 mg Q4W is optimally effective. In summary, characterization of AAER data from Study CD-RI-MEDI9929-1146 indicate the 210 mg Q4W dose provides improved efficacy over the 70 mg Q4W dose, whereas the 280 mg Q2W dose did not further reduce AAER. Tezelumab was well-tolerated at all doses and the safety profile was well balanced between the tezelumab and placebo groups with no evidence of a dose relationship to TEAEs in the adult population.

To ensure that the dose of 210 mg Q4W is an appropriate dose across adolescents from the age of 12 to 17 years old, PK simulations were conducted to compare exposures between adults and adolescents based on the adult body weight distribution from the phase 2b study and the adolescent body weight distribution from the Centers for Disease Control and Prevention growth charts (US).

The mean exposure in the adolescent population as a whole was found to be 1.67-fold higher in adolescents than in adults at the 210 mg Q4W dose. Compared to the overall variability in the PK of tezelumab (coefficient of variation [CV] approximately 45% to 50%), and the fact that tezelumab has been shown to be well-tolerated at the 280 mg Q2W dose (which resulted in approximately 2.7-fold higher exposure than at the 210 mg Q4W dose in adults), the adolescent exposures at the 210 mg SC dose are considered unlikely to pose a safety risk.

The dose of 210 mg SC Q4W has been selected for evaluation in both the adult and adolescent populations with a body weight of ≥ 40 kg.

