 - Nasal polyps in the 2 years before randomisation will be defined by the presence of nasal polyps on the Respiratory Disease History eCRF page for a particular subject, with no associated stop date on the Medical History eCRF or an associated stop date less than, or equal to 24 months before randomisation.
- Chronic sinusitis status at study entry: Yes, No

- Chronic sinusitis at baseline will be defined by the diagnosis of chronic sinusitis on the Respiratory Disease History eCRF page for a particular subject.
- Rhinitis status at study entry: Yes, No
- Rhinitis at baseline will be defined by the diagnosis of rhinitis on the Respiratory Disease History eCRF page for a particular subject.
- *Biomarker quartiles
- The four, mutually exclusive, biomarker quartiles will be derived using the baseline FENO, eosinophil and total serum IgE data. This will ensure that the same quartiles will be used for all endpoints analysed.
- #Weight quartiles
- The four, mutually exclusive, weight quartiles will be derived using the baseline weights.
- #Drug concentration exposure quartiles
- The four, mutually exclusive, quartiles will be derived using the median trough steady state drug concentration data. The median trough steady state is calculated as the median of the observed drug concentration data at weeks 24, 36 and 52 for each individual subject.

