4.2.4 Primary endpoint

4.2.4.1 Primary analysis

The primary analysis of the primary efficacy endpoint (AAER over 52 weeks) will quantify the effect of the initially randomised treatment, regardless of the treatments that subjects actually received, or whether the subjects received other controller therapy/rescue medications post IP discontinuation.

This analysis uses a treatment policy strategy and will therefore include all available data after treatment discontinuation until the end of the planned treatment period.

Subjects will be encouraged to continue to undergo applicable study related visits/procedures for the full 52-week period even after premature discontinuation of IP. Consequently, subjects lost to follow-up, subjects who die and subjects who withdraw their consent should be the only source of missing information for the primary analysis.

Missing data from early study withdrawal will be modelled based on what was observed during the study using direct likelihood approaches, which is a valid approach under the assumption that data are missing at random (MAR).

AAER in the tezepelumab group will be compared to that seen in the placebo group using a negative binomial model. This model will be used to perform the statistical test of the null hypothesis specified in [Section 4.1.1](#) and to estimate the treatment effect and both its 99% and 95% confidence intervals.

The response variable in the model will be the number of asthma exacerbations experienced by a subject over the 52-week planned treatment period (or shorter duration if not followed up

for the full 52 weeks). Treatment, region, age (adolescents or adults) and history of exacerbations (≤ 2 or > 2 in previous 12 months) will be included as factors in this model. Any subject who is incorrectly randomised with a history of fewer than 2 exacerbations will be included in the primary analysis. The logarithm of the time at risk (in years) for exacerbation will be used as an offset variable in the model, to adjust for subjects having different follow-up times during which the events occur. Time during an exacerbation and the 7 days following an exacerbation in which a new exacerbation cannot occur, will not be included in the calculation of time at risk for exacerbation. For all further primary endpoint derivation details, see [Section 3.2.1](#).

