4.2.5 Key secondary endpoints

4.2.5.1 Main analysis

The main analysis of the key secondary endpoints (changes from baseline to Week 52 for each of pre-bronchodilator FEV₁, AQLQ(S)+12 total score, ACQ-6 score and weekly mean ASD score) will quantify the effect of the initially randomised treatment at Week 52, regardless of the treatments that subjects actually received, or whether the subjects received other controller therapy/rescue medications, including for subjects who discontinued study treatment prior to Week 52.

This analysis uses a treatment policy strategy and will therefore include all available data after treatment discontinuation until the end of the planned treatment period.

Subjects will be encouraged to continue to undergo applicable study related visits/procedures for the full 52-week period even after premature discontinuation of IP. Consequently, subjects lost to follow-up, subjects who die, subjects who withdraw their consent and subjects who choose Option 3 for their follow-up should be the only source of missing information for the key secondary analyses apart from subjects who choose Option 2 for their follow-up, who will have missing pre-BD FEV₁ following discontinuing of IP until their Week 52 visit.

Missing data will be modelled based on what was observed during the study using direct likelihood approaches, which is a valid approach under the assumption that data are missing at random (MAR).

Change from baseline for the key secondary endpoints in the tezepelumab group will be compared to that seen in the placebo group using a mixed model for repeated measures (MMRM) model. This model will be used to perform the statistical tests of the null hypotheses specified in [Section 4.1.1](#), and to estimate the treatment effect at Week 52 and its 95% confidence interval, for each endpoint.

The response variable in the model will be change from baseline at each scheduled post-randomisation visit up to and including Week 52, and irrespective of whether the subject remained on treatment and/or took other treatments. Treatment, visit, region, age (adolescents or adults) and treatment by visit interaction will be included as factors in this model. Baseline of the corresponding endpoint will also be included in the model as a continuous linear covariate. Baseline by visit interaction will not be included as a covariate in the MMRM model.

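### The concentration-quartile exposure-response models carry no body weight term, so if weight is prognostic part of any gradient may reflect weight rather than exposure

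*SAP*

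**What the plan says.** SAP 3.1.7 defines each tezepelumab subject's exposure as a median trough, "calculated as the median of the observed drug concentration data at weeks 24, 36 and 52 for each individual subject", and cuts it into quartiles. In SAP 4.2.9.3 these quartiles and placebo become the treatment groups: "Each drug concentration quartile will be compared against the overall placebo group".

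For the exacerbation rate, "A similar negative binomial model will be fitted as for the primary analysis". The terms of that model in SAP 4.2.4.1 are "Treatment, region, age (adolescents or adults) and history of exacerbations", with log time at risk as offset. For lung function, "A similar MMRM model will be fitted as for the key secondary endpoint pre-BD FEV₁". SAP 4.2.5.1 states "Treatment, visit, region, age (adolescents or adults) and treatment by visit interaction will be included as factors in this model", and adds the baseline value of the endpoint. Body weight is in neither list. The weight-quartile analysis in the same section names its extra model terms; the concentration-quartile analysis names none.

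The dose is not scaled to weight. Protocol 4.3 states "The dose of 210 mg SC Q4W has been selected for evaluation in both the adult and adolescent populations", with a minimum weight of 40 kg. It compares adolescent and adult exposure by simulation from body weight distributions and reports: "The mean exposure in the adolescent population as a whole was found to be 1.67-fold higher in adolescents than in adults".

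**The concern.** The quartiles are formed after randomisation and in one arm only, so quartile-versus-placebo comparisons are not randomised. At a fixed dose, heavier subjects tend to have lower concentrations. The lowest quartile should therefore be heavier on average than placebo, and the highest quartile lighter.

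If weight also predicts exacerbations or FEV1 change independently of the drug, that imbalance enters the quartile estimates. It could create a gradient, exaggerate a real one or hide it, depending on the direction of the weight effect. The gradient is what the analysis is meant to describe.

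**Working it through.** **1. The plan's own figures.** These check the rate, dispersion and sample size reused below. Inputs from Protocol 9.2: 530 per arm, placebo rate 0.9, 50% reduction, shape parameter 2.4, 10% uniform dropout (mean follow-up about 0.95 year), two-sided 1%.

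- Variance of a log rate = (1/(rate × time) + dispersion)/n.
- Placebo: (1/0.855 + 2.4)/530 = 0.00674. Active: (1/0.4275 + 2.4)/530 = 0.00894. SE of the log rate ratio = √0.01568 = 0.125.
- Power = Φ(0.693/0.125 − 2.576) = 99.8%, against a stated figure above 99%.
- For the subgroup with eosinophils below 300/µL the same method gives 94.5% (stated 94%). Taking the dispersion as 1/2.4 would give 99.5%, so 2.4 is the dispersion itself.

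**2. How far concentration sorts by weight.** From Protocol 4.3: overall PK coefficient of variation (CV) 45-50%. Assumed, because the documents do not give them: log-normal weight centred at 80 kg with CV 20-25%, and exposure proportional to weight to the power −0.75 to −1.

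- SD of log concentration = √ln(1 + CV²) = 0.429 to 0.472. SD of log weight = 0.198 to 0.246.
- Correlation = −exponent × SD(log weight)/SD(log concentration). Weakest: −0.75 × 0.198/0.472 = −0.31. Strongest: −1 × 0.246/0.429 = −0.57.
- Squared, weight explains 10-33% of log-concentration variance.
- The mean normal score in an extreme quartile is ±1.271, so typical weight = 80 × exp(±|correlation| × 1.271 × SD(log weight)). This gives 86.6 against 73.9 kg at the weak end and 95.7 against 66.9 kg at the strong end, a gap between lowest (Q1) and highest (Q4) quartile of about 13-29 kg.

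**3. Spurious factor between Q1 and Q4 with no exposure effect.** Assumed: exacerbation rate rises by a fixed percentage per 10 kg. Factor = (1 + percentage)^(gap/10).

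- 0% per 10 kg: 1.0.
- 3%, weak end: 1.03^1.27 = 1.04.
- 5%: 1.05^1.27 = 1.06 to 1.05^2.89 = 1.15.
- 10%, strong end: 1.10^2.89 = 1.32.

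If the rate falls with weight, the direction reverses.

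**4. Check by simulation.** True rate ratio 0.5 in every quartile, weight CV 25%, exponent 1, concentration CV 47.5%, 530 per arm, dispersion 2.4. One SD of log weight is about 0.246 × 80 = 20 kg, so 1.1-fold per SD is roughly 5% per 10 kg and 1.2-fold roughly 10%.

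| Rate per SD of log weight | Q1 to Q4 rate ratios without weight | Q4/Q1 | Q4/Q1 with weight in model |
|---|---|---|---|
| 1.0 | 0.50, 0.49, 0.50, 0.50 | 1.01 | 1.01 |
| 1.1 | 0.53, 0.50, 0.49, 0.47 | 0.88 | 1.01 |
| 1.2 | 0.56, 0.51, 0.48, 0.43 | 0.77 | 1.00 |

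The reciprocals 1/0.88 = 1.14 and 1/0.77 = 1.30 agree with step 3.

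**5. Size against noise.** With about 132 subjects per quartile, the variance in one quartile is (1/0.4275 + 2.4)/132 = 0.0359. The SE of the Q1-versus-Q4 log ratio is √(2 × 0.0359) = 0.27, so its 95% interval spans a factor of exp(1.96 × 0.27), about 1.7, either way. A spurious factor of 1.06-1.15 is 0.2-0.5 SE; 1.32 is about 1 SE.

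**The case against.** Several points on the other side stand.

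- **The bias needs weight to be prognostic.** Neither document says that it is. If it is not, the unadjusted analysis shows no bias, as the first simulation row confirms.
- **Weight explains only a minority of concentration.** On the assumptions above, 67-90% of log-concentration variance has other sources. A reader might infer that sorting by concentration amounts to sorting by weight; that is too strong.
- **The effect is small against noise**, and SAP 4.2.9.3 plans estimates, intervals and plots, with no trend test.
- **Adjustment is partial.** Missed doses, discontinuation, anti-drug antibodies and clearance differences unrelated to weight also affect observed concentration. Adding weight does not restore a randomised comparison.
- **Other exposure modelling is planned.** Protocol 9.4.5 reports population PK and pharmacodynamic analyses separately. The documents do not say whether those adjust for weight, so it cannot be inferred that the programme ignores it.

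Two defences do not answer the point. The weight-quartile analysis compares randomised arms within weight groups and may show whether weight is prognostic, but it leaves the concentration-quartile estimates unadjusted. The adult/adolescent factor covers a contrast involving about 80 of 1060 subjects, so weight variation among adults remains. Baseline FEV1 in the MMRM may absorb some imbalance for that endpoint, whose possible bias has not been quantified here.

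**Conclusion.** The point holds as a minor improvement to an exploratory analysis. No weight term is specified, exposure at the fixed dose is tied to weight by the protocol's own simulations, and the comparison is non-randomised. With no true exposure effect, the spurious factor between extreme quartiles runs from 1.0 to about 1.06-1.15 at 5% per 10 kg, and to 1.32 at 10% per 10 kg with the strongest assumed weight-concentration link. The weight distribution, the exponent and the prognostic effect are all assumptions, and the last is decisive. A bias of this size would usually lie within sampling error, but four ordered points on a forest plot can still be read as a trend.

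Two stronger readings are not supported. A reader might infer that the analysis is there to justify one dose across body weights; SAP 4.2.9.3 gives its purpose only as describing the exposure-response relationship. A reader might also infer a threat to the trial's main result; the analysis is outside the testing hierarchy of SAP 4.1.2, so type I error and the primary conclusion are untouched.

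**What to change.** In SAP 4.2.9.3:

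1. Add baseline body weight, as a continuous covariate, to the concentration-quartile negative binomial model and the concentration-quartile FEV1 MMRM.
2. Tabulate baseline weight for each concentration quartile and for placebo beside the forest plot.
3. State that the quartile-versus-placebo comparisons are non-randomised and that other determinants of concentration remain unadjusted, so that the adjusted gradient is not read as causal.

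Weight is already measured at Visit 1, and SAP 3.1.7 already uses baseline weight for the weight quartiles. The cost is one extra model term, one small table and one sentence, with slightly wider intervals because weight and concentration are correlated.
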